#### **2.1.1. Primary Objectives**

- To determine the effect of intranasal oxytocin (Syntocinon®) on brain activity associated with social rewards using fMRI.
- To assess the effects of intranasal oxytocin (Syntocinon®) on the neural processing of non-social (i.e. monetary) rewards.
- To determine whether the neural responses to social cues and rewards are altered in recently abstinent persons with AUD.
- To determine whether the effect of intranasal oxytocin (Syntocinon®) on brain activity associated with social cues and rewards differs between control participants and recently abstinent persons with AUD.

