## **3. STUDY DESIGN**

This is a double-blind, placebo-controlled, randomized study of the effects of Syntocinon® on brain activity elicited during the processing of reward. Each participant will be studied twice using fMRI; once self-administering Syntocinon® and once self-administering placebo intranasally approximately 30 minutes prior to being scanned. Participants will be randomly assigned to self-administer either Syntocinon® or placebo first. Scans will be performed on separate days approximately 1-2 weeks apart.

Participants will be evaluated thoroughly at screening for eligibility and will only be entered into the study if they meet all inclusion criteria and none of the exclusion criteria.

88 participants are planned to complete the study (44 controls, 44 AUD). Total duration of the study is expected to be 60 months.

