### **4.2. Inclusion Criteria**

General Inclusion Criteria for All Participants:

- 18-45 years of age at the time of screening
- No current or past history of neurological illness
- No acute medical illness

Additional Inclusion Criteria for Control group:

- No current or past history of psychiatric illness, including substance use disorder (except nicotine)

Additional Inclusion Criteria for AUD group:

- Meet DSM-5 criteria for current moderate-to-severe AUD
- Abstinent from alcohol for 2-8 weeks prior to study enrollment
- Express a desire to achieve abstinence or to greatly reduce alcohol consumption

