## 8.2. Analysis of Primary Endpoint

### 8.2.1. fMRI Data Processing.

**Preliminary processing.** All fMRI data will be submitted to an initial series of preprocessing steps (e.g. slice-timing correction, realignment, artifact checks). The functional data acquired for each subject will be coregistered to the structural image collected and finally warped into standardized space using specialized neuroimaging software (e.g. Statistical Parametric Mapping software [SPM8, Wellcome Department of Cognitive Neurology, University College, London, UK]).

**Subject-level analysis.** For each task (for both Syntocinon® and Placebo conditions), a general linear model will be constructed with parameters corresponding to the anticipation and outcome of each type of reward at stake, modeling each session separately. Each stimulus type will be convolved with the hemodynamic response function to assess task-related changes in BOLD signal. Contrasts will be constructed to test for BOLD differences in anticipation activity (anticipation of reward vs null) and outcome activity (outcomes for reward trials versus outcomes for null trials) for each reward type. The statistical maps generated by these analyses will then be slightly smoothed and introduced into second level-analyses.

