### 8.2.2. Data Analysis & Anticipated Results.

**Analysis of Primary Objective 1 and 2.** Examine the effects of oxytocin on the modified monetary and social incentive delay tasks.

*Analyses.* We will conduct whole-brain voxel-wise analyses with drug (Syntocinon® or Placebo) as a within-subject factor. We will examine the main effects of drug on reward related BOLD activity across the brain during both anticipation and outcome phases.

*Anticipated Results.* As oxytocin administration has been previously demonstrated to reduce amygdala activity in response to social challenges it is hypothesized that we will see a blunting of amygdala reactivity during the anticipation and attainment of social rewards (particularly for negative social incentives). Oxytocin has also been demonstrated to increase dopaminergic activity within the mesolimbic dopamine system (20) so we may see an enhancement of ventral striatal activity during the anticipation of social rewards; however, as Knutson and collaborators have reported that inducing dopamine release within the ventral striatum by amphetamine can actually reduce the difference in BOLD signal activity seen between the anticipation of reward and the anticipation of null (51), reductions in the BOLD response to anticipation of social reward within the ventral striatum is also possible.

While oxytocin has been predominately noted to affect social processes, there is some data to suggest that oxytocin's effects extend beyond modulating affiliative behaviors. Given this, we hypothesize oxytocin administration will show similar, though perhaps diminished, effects on amygdala and ventral striatal activity in response to the anticipation of monetary rewards as we see in anticipation of social rewards.

**Analysis of Primary Objective 3.** Compare responses to the modified monetary incentive delay task in participants with AUD versus controls.

*Analyses.* We will conduct whole-brain voxel-wise analyses with group (AUD or Control) as a within-subject factor. We will examine the main effects of group on reward related BOLD

activity across the brain during both anticipation and outcome phases.

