*Anticipated Results.* It has been observed that individuals with AUD or with a family history of alcoholism show blunted NAc activity during the anticipation of non-drug rewards which may reflect a bias towards alcohol related stimuli. Both the insula and ACING are also implicated in the neurobiology of AUD. Indeed, lower insular activity has been demonstrated to be predictive of relapse and ACING responsivity to the anticipation of monetary reward is inversely related to characteristics associated with AUD including impulsivity. Hence, we expect to observe lower BOLD responses to the anticipation of rewards within the NAc, insula and ACING, in the AUD group compared to controls.

**Analysis of Primary Objective 4.** Compare the effects of oxytocin on the modified monetary incentive delay task in participants with AUD versus controls.

*Analyses.* We will conduct whole-brain voxel-wise analyses with drug (Syntocinon® or Placebo) and group (AUD or Control) as within-subject factors. We will examine the main effects of drug on reward related BOLD activity across the brain during both anticipation and outcome phases and compare this activity between groups.

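### Section 8.2.2 makes group (AUD or control) a within-subject factor for Primary Objectives 3 and 4, although no participant can belong to both groups

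*Protocol*

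**What the plan says.** Section 8.2.2 of the protocol gives the group-level model for each primary objective. For Objectives 1 and 2, drug is the within-subject factor, which suits the crossover. For Objective 3 the text reads "We will conduct whole-brain voxel-wise analyses with group (AUD or Control) as a within-subject factor". For Objective 4 it names drug "and group (AUD or Control) as within-subject factors", and then says the drug effects will be examined "and compare this activity between groups".

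The design is set out elsewhere in the protocol. Section 3 plans for 88 completers, 44 controls and 44 with AUD, each scanned once on Syntocinon and once on placebo. Under section 4.2 a control may have no psychiatric history, which includes any substance use disorder other than nicotine, whereas a participant with AUD must "Meet DSM-5 criteria for current moderate-to-severe AUD". Section 2.1.1 words Objective 4 as whether the oxytocin effect "differs between control participants and recently abstinent persons with AUD". Section 8.2.1 builds the subject-level models "modeling each session separately", so each person supplies a map per session for each contrast.

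**The concern.** A within-subject factor is one whose levels are all observed in the same person. Drug meets that definition. Group does not: nobody can satisfy both sets of entry criteria, and the protocol describes no matching of AUD participants to controls. The stated model therefore does not fit the design for two of the four primary objectives.

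The label matters because it determines which variance the group effect is tested against. A group difference must be judged against variation between people. An analyst who follows the text has three routes: test group against within-person error, treat unrelated people as repeated measures on one subject with a pooled error, or pair unrelated people and give each effect its own error term. The first two can produce false AUD-control differences. The third is valid but arbitrary. An analyst who avoids all three departs from the protocol.

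**Working it through.** **Does each factor vary within a person?**

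| Factor | Section 8.2.2 | Sections 3 and 4.2 | Correct type |
|---|---|---|---|
| Drug | within-subject | each person scanned on both | within |
| Group | within-subject | 44 and 44 different people, exclusive criteria | between |

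This settles the labelling error without any arithmetic. The rest sizes the consequences.

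**Inputs.** From the protocol: 44 per group and two scans per person (section 3); one-sided threshold 0.005 and effect size 0.77 SD (section 8.1). Assumed: unit variance per scan and between-session correlation r of 0.3, 0.5 or 0.7, since the protocol gives none. The threshold comes from the region-of-interest power calculation, because section 8.2.2 states no whole-brain threshold.

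**The plan's own figure.** Section 8.1 claims at least 90% power with 44 subjects at 0.77 SD. A one-sample or paired t test with n = 44 gives 99.0%; a two-sample t test with 44 per group gives 83.3%. The text does not say which contrast is meant. That is a separate matter, and 0.77 serves here only as an effect size.

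**Group effect, both sessions entered, tested against within-person error.** The true variance of the group difference in person means is (1+r)/44. The within-person error assigns it (1−r)/44. The ratio is (1+r)/(1−r), and the approximate type I error is P(Z > 2.576/√ratio).

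**Group effect, unrelated people stacked as one subject, pooled error.** The expected pooled mean square is [(1+r) + 2(1−r)]/3 = (3−r)/3, which is 0.90, 0.83 and 0.77. The ratio is (1+r) divided by this.

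| Type I error for group, nominal 0.5% | r = 0.3 | r = 0.5 | r = 0.7 |
|---|---|---|---|
| Within-person error: ratio | 1.86 | 3.00 | 5.67 |
| – approximation | 2.9% | 6.8% | 14.0% |
| – simulation | 2.8% | 6.5% | 13.4% |
| Stacked, pooled error: ratio | 1.44 | 1.80 | 2.22 |
| – approximation | 1.6% | 2.7% | 4.2% |
| – simulation | 1.6% | 2.6% | 4.0% |
| Arbitrary pairs, own error term (43 df), simulation | 0.5% | 0.5% | 0.5% |
| Correct two-sample test (86 df), simulation | 0.5% | 0.5% | 0.5% |

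The simulations used 100,000 null trials per setting. If only one session enters Objective 3, the literal model reduces to arbitrary pairing and type I error is 0.5%. At a two-sided 5% level, a separate simulation of the within-person-error test gave about 15%, 26% and 40%.

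**Drug-by-group effect (Objective 4).** Its true error is (1−r). Against the pooled (3−r)/3 the ratio is 0.78, 0.60 and 0.39, so the test is conservative: type I error 0.2%, 0.05% and below 0.01%. It is 0.5% with the correct test and with arbitrary pairs.

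**Power for Objective 4** at 0.77 SD of the drug-difference map. The noncentrality is 0.77 × √(44/2) = 3.61.

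- Correct two-sample test, 86 df: 83.3%.
- Arbitrary pairs, 43 df: 81.5%.
- Stacked with pooled error (simulation, 50,000 trials per setting): 74%, 60% and 30%. The approximation P(Z > 2.576/√ratio − 3.61) gives about 76%, 61% and 31%.

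**The case against.** The strongest reply is that the phrase was carried over from Objectives 1 and 2, where it is right for drug, and that the intent is plain. The text around it speaks throughout of AUD participants compared with controls, and Objective 4 ends with a comparison between groups. A competent analyst would fit a two-sample comparison regardless. This stands as an account of how the error arose and limits its seriousness. It does not remove it: the wrong label appears twice, and no other part of the protocol states the correct factor structure.

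The second reply is that the large figures are conditional. This also stands. Inflation needs both sessions in the model and the wrong error term, and it affects only the group effect of Objective 3. The protocol does not say that both sessions enter that analysis. The correlations are assumed and the threshold is borrowed. Objective 4 carries at most a loss of power.

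Third, comparing the drug effect between groups already is a drug-by-group interaction in substance, and the formal contrast, like the choice of session for Objective 3, can be left to a statistical analysis plan. That is fair, and the finding does not rest on either point. A wrongly stated factor is different: an analysis plan that followed it would inherit the error, and one that did not would contradict the protocol.

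Lastly, the 83% should not be read as harm from the label. It is the power of the correct test at a borrowed effect size; only the drop below it is attributable.

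**Conclusion.** The concern holds. Section 8.2.2 is wrong as written for Primary Objectives 3 and 4: group is a between-subject factor and only drug is within-subject. This follows from sections 3 and 4.2 and rests on no assumed number.

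The consequence ranges from almost nothing to serious. With arbitrary pairs and a separate error term, type I error is kept and Objective 4 power falls only from 83.3% to 81.5%. If both sessions enter and group is tested against within-person error, the false-positive rate for an AUD-control difference rises from 0.5% to between 2.8% and 13.4% over the assumed correlations of 0.3 to 0.7. The drug-by-group test is not inflated in any version examined, but loses substantial power under a pooled error. The point should be fixed; given the evident intent, it does not threaten the design.

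**What to change.** In section 8.2.2, state for Objectives 3 and 4 that group is a between-subject factor and, for Objective 4, that drug is a within-subject factor.

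- **Objective 3:** a two-sample comparison of one summary map per participant (86 df). It would help to say which session or sessions form that map.
- **Objective 4:** a two-sample comparison of each participant's Syntocinon-minus-placebo map (86 df), preferably named as the drug-by-group interaction.

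The cost is a wording change in one section. No new data, visits or participants are needed.

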## **8. DATA ANALYSIS/STATISTICAL METHODS**

### **8.1. Sample Size Determination**

Work done by Knutson, Spreckelmeyer and Rademacher, indicate that significant task effects can be observed in the incentive delay task in samples in the range of 15-18 participants [34,35,37,38]. We implemented an fMRI-based power analysis using the fMRIpower software package (fmripower.org). The effect sizes below are expressed in standard deviation units, which is analogous to the Cohen *d* measure. All power calculations are based on ROIs with a p-value threshold of 0.005 for a 1-sided hypothesis test. With 44 subjects, we will have at least 90% power to detect an effect of size 0.77 in the nucleus accumbens, a region known to play a significant role in the processing of rewards [39,40].

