*Anticipated Results.* We expect the oxytocin intervention to have a larger effect on BOLD responses to the anticipation of social rewards on individuals with AUD for several reasons. First, it is hypothesized that individuals with social impairments, which are common in persons diagnosed with substance dependence, may receive greater benefit from exogenous oxytocin. Second, it is proposed that circulating levels of oxytocin may moderate how a given individual response to exogenous administration of oxytocin. Lower plasma oxytocin levels have been noted in individuals with substance dependence and morphological abnormalities have been noted in the oxytocinergic neurons of individuals with AUD. Finally, though oxytocin is known to impact social reward processing, it also may influence reward activity more generally. To explore the selectivity of oxytocin's effects, I will analyze anticipatory reward activity in regions identified as significant in the group analyses above and compare SID and MID activity. While we expect specific effects of oxytocin on the SID, if oxytocin was shown to influence reward activity irrespective of social content, this would indicate an exciting, broad role of oxytocin in reward in AUD. This would be of great interest to those seeking to utilize oxytocin to treat AUD, where reward dysfunction is known to play a key role.

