### **8.2.3. Potential Pitfalls and Alternative Strategies.**

- We will employ a more sensitive technique, called region-of-interest analyses, to detect potential variation in these conditions. Region-of-interest (ROI) analysis involves looking for changes within selected brain areas, instead of looking for changes across the whole brain. As a relatively smaller number of regions will be examined, the overall number of comparisons will be reduced, resulting in an increase in statistical power. Thus, subtle differences between the conditions can be identified. For our purposes, these ROIs would include the ventral striatum, the amygdala and thalamus.
- Humans are not a homogenous group, thus inter-individual variability may pose some difficulty in discerning effects. Variables such as age can have an impact on task parameters. To address this concern, we will (1) perform regression analyses to determine if there is a relationship between these variables and the contrasts of interest and (2)

perform an analysis of covariance (ANCOVA) to control for these variables. The inclusion of covariates in our analyses will increase overall statistical power as variability will be taken into account. In addition, as some groups have reported certain affiliative characteristics to be related to oxytocin measures, we will also be obtaining measures of attachment and sociability that can be used to help explain some of the variation.

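### The exploratory SID-versus-MID comparison uses only regions already significant in the same participants' data, with no requirement that selection be neutral between the two tasks

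*Protocol*

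**What the plan says.** Under the anticipated results for Primary Objective 4 (protocol section 8.2.2), the selectivity question is to be explored thus: "I will analyze anticipatory reward activity in regions identified as significant in the group analyses above and compare SID and MID activity". The same paragraph says how the answer would be read: either effects specific to the social task, or a broad role in reward.

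Four other places bear on which analyses would do the selecting:

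- Section 8.2.1 builds the subject-level contrasts separately by task, for example "outcome activity (outcomes for reward trials versus outcomes for null trials) for each reward type". No map combining SID and MID is described.
- Section 8.2.2, Objectives 1 and 2, plans whole-brain drug analyses of both tasks. For Objective 3 it says "We will examine the main effects of group on reward related BOLD" activity.
- The Objective 4 analysis is headed "Compare the effects of oxytocin on the modified monetary incentive delay task in participants with AUD versus controls", so it names the monetary task. Its expected result is about the social one: "We expect the oxytocin intervention to have a larger effect on BOLD responses to the anticipation of social rewards on individuals with AUD".
- Section 8.2.3 plans region-of-interest analyses and says "these ROIs would include the ventral striatum, the amygdala and thalamus". It does not tie them to the SID-versus-MID comparison.

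The only numerical threshold is in section 8.1: "All power calculations are based on ROIs with a p-value threshold of 0.005 for a 1-sided hypothesis test". The only effect size is there too: with 44 subjects, "at least 90% power to detect an effect of size 0.77 in the nucleus accumbens".

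**The concern.** A region that has just passed a significance test on one task tends to show that task's effect as larger than it truly is. The other task's effect in the same region is inflated less, in proportion to the correlation between tasks. Comparing the two there can produce a difference that reflects the choice of region and not the drug.

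The protocol fixes selection and comparison in the same participants. It does not fix that selection be even-handed between the tasks, and contrasts built by reward type make selection on one task's map a plausible reading.

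The comparison bears on a question in the Protocol Summary, namely whether oxytocin acts on reward in general or only when the reward is social. If drug effects are small, the answer could partly depend on which map chose the regions.

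**Working it through.** **The plan's own figure.** Noncentral t, one-sided 0.005, d = 0.77:

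- One-sample or paired, n = 44: noncentrality 0.77 × √44 = 5.11, power 99.0%.
- Two groups of 44: noncentrality 0.77 × √22 = 3.61, power 83.3%.

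The stated lower bound of 90% therefore holds for a paired contrast and not for a 44 v 44 one. Section 8.1 does not say that 0.77 is a drug effect or a between-group difference in drug effect. Using it for either is an assumption here.

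**Inputs.** From the protocol: 44 per group, 0.005 one-sided, 0.77. Assumed: equal true SID and MID effects (so any difference found is false), d = 0.2 to 0.3 as small effects, unit SDs, correlation ρ between the tasks' drug effects of 0.3 to 0.6, and a two-sided 5% test of SID minus MID. The 0.005 is the power-calculation threshold, borrowed here as the selection cut-off.

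**Mechanism by hand (paired, n = 44, d = 0.2).**

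1. Selection needs an observed effect above t(0.995, 43)/√44 = 2.695/6.633 = 0.406 SD, twice the true value.
2. With a = (0.406 − 0.2) × 6.633 = 1.37, the expected excess in the selecting task is about [φ(a)/(1 − Φ(a))]/√44 = (0.1565/0.0857)/6.633 = 0.275 SD.
3. The other task carries ρ times that excess, so the spurious gap is (1 − ρ) × 0.275, which is 0.19 SD at ρ = 0.3 and 0.11 SD at ρ = 0.6.

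Simulation with estimated SDs gives 0.18 and 0.10.

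**Simulation.** 1,000,000 regions per setting. Entries are the percentage of selected regions declared different; each range covers ρ = 0.3 to 0.6.

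| Selected on (0.005) | True d | Paired, n=44 | Drug-by-group, 44 v 44 |
|---|---|---|---|
| One task | 0.2 | 9.6–13.4 | 12.4–18.5 |
| One task | 0.3 | 6.9–8.0 | 9.4–12.4 |
| One task | 0.5 | 4.2–4.5 | 5.6–6.0 |
| One task | 0.77 | 4.7–4.9 | 4.0–4.4 |
| Either task | 0.2 | 11.8–15.0 | 14.6–20.0 |
| Either task | 0.3 | 8.8–9.6 | 11.5–14.1 |
| SID/MID average | 0.2–0.77 | 4.9–5.1 | 4.9–5.1 |

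- *Direction.* For one-task selection at d = 0.2 to 0.3, 94 to 99.7% of the false differences (paired) and at least 98% (drug-by-group) favour the selecting task. The mean spurious gap is 0.07 to 0.18 SD and 0.14 to 0.30 SD. For either-task selection the false differences split about evenly.
- *Frequency.* Regions with d = 0.2 to 0.3 are selected in 9.7 to 25% of cases (paired) or 4.9 to 12% (drug-by-group). Multiplying by the error rates (for example 0.254 × 0.080 = 0.020), about 1 to 2% and 0.6 to 1.5% are both selected and falsely different.
- *Groups pooled (n = 88), one task, d = 0.2 to 0.3.* 4.6 to 8.5%.
- *Selection on the group main effect.* 4.9 to 5.2%, so no problem.
- *Stricter assumed cut-offs at d = 0.77, one task.* Drug-by-group selection gives about 7.5 to 9% at p < 0.00001 and 10 to 14% at p < 0.000001. Paired selection gives about 5% and 6%.

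**The case against.** The strongest objection is that which contrast defines a region is detail for a statistical analysis plan, and that plan is not at hand. This stands in part: the protocol does not say that one task's map selects, and some readings are harmless. But the protocol does state the rule of selecting by significance in the same data, and that rule admits readings that are not harmless.

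Second, the magnitude rests on assumed small effects, an assumed correlation and an assumed test level. That is so, and few small-effect regions would be selected at all. Section 8.2.2 does, however, allow that the monetary effects may be the weaker ones, and it leaves the direction in the ventral striatum open, so effects below 0.77 are worth examining.

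Third, section 8.2.3 already plans analyses in named regions. Those would avoid the problem if they were used for this comparison, which the text does not say.

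Two stronger readings are tempting and unsupported:

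- *That the plan is tilted toward finding a social-specific effect.* If the Objective 4 heading governs selection, the monetary task selects and the bias runs against the protocol's expectation. If regions from either task are used, there is no fixed direction.
- *That the trial's main conclusions are compromised.* The step is worded as exploratory and is not one of the four listed objectives.

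The opposite reading, that 0.77 settles the matter, is also too strong. It holds at the 0.005 cut-off, but the protocol gives no whole-brain threshold, and a strict one brings the inflation back for drug-by-group selection.

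**Conclusion.** The concern holds as a conditional one, at low severity. Comparing SID with MID in regions chosen by significance in the same participants can mislead unless the choice is neutral between the tasks, and the protocol does not require that.

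Under the stated assumptions with small effects, one-task selection raises a nominal 5% error to about 7 to 14% (paired) or 9 to 18% (drug-by-group), almost all of it in favour of the selecting task. Either-task selection raises it to about 9 to 20% with no fixed direction. Averaged selection with similar SDs, or selection on the group main effect, leaves it at 5%. At 0.77 SD and 0.005 there is no inflation.

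The documents do not settle which case applies, so neither the presence nor the direction of a bias in this trial can be asserted.

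**What to change.** Replace the selectivity sentence in section 8.2.2 with wording such as: 'To explore selectivity, the Syntocinon-minus-placebo difference in anticipatory activity will be compared directly between SID and MID (drug-by-task; drug-by-task-by-group for the AUD question) in anatomical regions of interest fixed before unblinding: ventral striatum including NAc, amygdala, thalamus, insula and ACING. Any further regions will be selected on the average of the SID and MID contrasts and reported descriptively.'

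The first three regions are those of section 8.2.3. Insula and ACING are added because section 8.2.2 names them, with NAc, as regions where the AUD group is expected to differ. Data-driven regions stay descriptive because averaging is neutral only when the tasks have similar SDs: at an assumed SD ratio of 1.25 the error is 5.3 to 6.8% (paired) or 6.0 to 7.7% (drug-by-group).

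The cost is wording and a small analysis change, with no new data. Regions outside the list are left to descriptive maps, and five regions add comparisons. By noncentral t, 80% power at two-sided 5% needs a standardized SID–MID difference in drug effect of 0.43 (paired, n = 44) or 0.60 (44 v 44). If the 5% were split equally over five regions (5%/5 = 1% each, an assumed rule), these become 0.54 and 0.74. The test can detect only moderate differences, so a null result should not be read as proof of a general effect.
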